PR	Partial response
Qd	Probability of dose being the MTD
RECIST	Response Evaluation Criteria in Solid Tumors
RMAD	Relative Median Absolute Difference
ROW	Rest of the world
RP2D	Recommended Phase II dose
SAE	Serious adverse event
SAP	Statistical Analysis Plan
SAS	Statistical Analysis System
SCCHN	Squamous cell carcinoma of the head and neck
SD	Stable disease
SD	Standard deviation
sqNSCLC	Squamous non-small cell lung cancer
Td	(Tolerable) Probability that the DLT rate is <0.20 , $Pr(p <0.20 d)$, for a dose d
TEADR	Drug-related adverse event
TEAE	Treatment-emergent adverse event
t_{last}	Time to last observed concentration
t_{max}	Time to maximum observed concentration
TTP	Time to progression
vs	Versus, as opposed to
WHO DD	World Health Organization Drug Dictionary

1. Introduction

Fibroblast growth factors (FGF) and their corresponding receptor family (FGFR) drive crucial oncogenic signaling pathways including cell proliferation, survival and migration. FGFRs are commonly altered in various human tumor diseases, including FGFR1 amplification in squamous non-small cell lung cancer (sqNSCLC) or activating mutations of FGFR3 in bladder cancers. These changes contribute to tumor cell growth, sustained angiogenesis, invasion and metastasis and resistance against other therapies.

Rogaratinib (BAY 1163877) is an oral inhibitor of FGFR1, 2 and 3 and showed strong anti-tumor efficacy in pre-clinical models as a single agent as well as in combination with cytotoxic agents in FGFR pathway addicted tumor models.

The targeted application form is oral and preclinical data suggest low clearance and low volume of distribution resulting in a daily dose of 300 to 800 mg.

Further details can be found in the investigator's brochure (IB) (1), which contains comprehensive information on the study drug. The IB is available in the Trial Master File.

Additional information elaborating on the rationale of the study and the benefit-risk assessment can be found in the protocol.

This Statistical Analysis Plan (SAP) is based on the Clinical Study Protocol version 7.0 (including Amendment 7.0) (2).

2. Study Objectives

The primary objectives of this study are:

- To determine the safety and maximum tolerated dose (MTD) of BAY 1163877 in subjects with advanced solid organ malignancies

Statistical Analysis Plan

Protocol No.: **BAY 1163877/16443**

Page: 5 of 20:

- To characterize the pharmacokinetics (PK) of BAY 1163877

The secondary objectives of this study are:

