- To evaluate biomarker status, pharmacodynamic (PD) parameters, and tumor response.
- To assess the relative bioavailability of the tablet formulation in comparison to the solution formulation of BAY 1163877.

The exploratory objective of this study is:

- To evaluate selected immune parameters.

3. Study Design

This is a Phase I, first-in-human, open-label, non-randomized, multi-center, 3-part, dose escalation study of BAY 1163877 in sequential cohorts of subjects with refractory, locally advanced or metastatic solid tumors. The study will be conducted at multiple centers worldwide.

Study Part 1 will identify the MTD in subjects with any solid tumors (all comer) using an adaptive dose escalation design and expansion of cohort at MTD.

Study Part 2 will explore further the safety and PD of BAY 1163877 at the MTD identified in Part 1 in subjects with sqNSCLC, LAC, BC, and SCCHN to seek any evidence of preliminary clinical responses. Study Part 2 may start as soon as the MTD has been established in Part 1.

Study Part 3 will expand the safety database for patients on treatment with BAY1163877 at the MTD identified in Part 1 with sqNSCLC, LAC, and BC. In parallel, in Part 3 additional efficacy data will be collected and changes of selected immune parameters will be assessed.

The complete duration of the study (Part 1, Part 2, and Part 3) depends on the number of dose escalation steps in Part 1 and will be approximately 7 years.

Planned sample size:

Subjects will be enrolled in the pre-treatment phase of the study to recruit enough subjects with present high FGFR expression levels for the following study parts.

Targeted / planned enrollment:

- Study Part 1 / dose escalation (all comer): The total number of subjects will depend on the number of cohorts necessary to identify the MTD. Relative bioavailability of the tablet formulation in comparison to the solution formulation will be performed in all subjects enrolled in one of the dose escalation cohorts; pharmacokinetic data are needed in a minimum of 3 subjects for relative bioavailability assessment.
- Study Part 1 / MTD expansion (all comer): Additional subjects will be enrolled to have 20 evaluable “all comer” subjects treated at MTD.

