Treatment: Subjects with PK assessment (all subjects of study Part 1 and 3 and at least 12 subjects of study Part 2 and approximately 8 subjects of the MTD expansion cohorts with impaired renal function at baseline) will receive BAY 1163877 (tablet or solution) on a continuous schedule starting with single-dose administration on Cycle 1, Day 1, followed by a “drugfree day” (to enable single dose PK assessments except for subjects in Part 3 who will receive BAY 1163877 twice daily continuously with no “drug free day”). Treatment with BAY 1163877 will resume on Day 3 of Cycle 1 if no protocol-defined dose-limiting toxicities (DLTs) are reported. Starting on Cycle 1, Day 3, the study drug will be self-administered twice daily for the remaining 19 days of Cycle 1. For subsequent cycles, study drug will be administered twice daily for 21 days until disease progression or as long as clinical benefit is assumed by the investigator or until unacceptable toxicity occurs.

In one of the dose escalation cohorts in study Part 1 (“tablet bridging cohort”), relative bioavailability of the tablet formulation will be assessed by administration of a single dose of the tablet formulation on Cycle 1, Day -3. Starting with Cycle 1, Day 1, subjects enrolled in the “tablet bridging cohort” will continue with the solution formulation as described above. Depending on the results from the relative bioavailability assessment, subjects who initially start with solution formulation may be switched to tablet formulation in later cycles.

Approximately 8 subjects enrolled in the MTD expansion cohorts (study Part 1 and Part 2) will receive single doses of BAY 1163877 on Cycle 1, Day -3, after consumption of a high-fat, high-calorie breakfast and on Cycle 1, Day 1, after an overnight fast of at least 8 hours followed by treatment according to the schedule described above starting on Cycle 1, Day 3.

Subjects without PK assessment in study Part 2 will receive BAY 1163877 (tablet or solution) twice daily from Cycle 1, Day 1 ongoing.

At home, subjects will document the intake of study drug in a diary.

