4.1 General Principles

The statistical evaluation will be performed by using the software package SAS release 9.2 or higher (SAS Institute Inc., Cary, NC, USA), R release 2.4.1 or higher and BRugs release 0.3-3 or higher. All variables will be analyzed by descriptive statistical methods. The number of data available, mean, standard deviation, minimum, median, and maximum will be calculated for metric data. Frequency tables will be generated for categorical data.

Data displays will follow the standard table catalogs for oncology standards, global standards, and clinical pharmacology standards, respectively.

The pharmacokinetic parameters will be evaluated statistically in accordance with pertinent company guidelines.

The following treatment groups will be analyzed:

- Total Dose Escalation – It contains all cohorts from the escalation phase:
 - 100 mg BAY 1163877 (50 mg solution BID)
 - 200 mg BAY 1163877 (100 mg solution BID)
 - 400 mg BAY 1163877 (200 mg tablet BID)
 - 800 mg BAY 1163877 (400 mg tablet BID)
 - 1200 mg BAY 1163877 (600 mg tablet BID)
 - 1600 mg BAY 1163877 (800 mg tablet BID)
- Expansion All Comers – Expansion phase, 1600 mg BAY 1163877 (800 mg tablet BID), cancer type does not fit the categories below
- Expansion Bladder – Expansion phase, 1600 mg BAY 1163877 (800 mg tablet BID), cancer type: bladder cancer

Statistical Analysis Plan

Protocol No.: **BAY 1163877/16443**

Page: 11 of 20:

- Expansion Head & Neck – Expansion phase, 1600 mg BAY 1163877 (800 mg tablet BID), cancer type: squamous carcinoma cell head and neck
- Expansion NSCLC – Expansion Phase, 1600 mg BAY 1163877 (800 mg tablet BID), cancer type: lung adenocarcinoma / squamous cell carcinoma

The categories of region used for subgroup analysis will be derived for each subject by using the variable country (location of the respective site).

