6.3 Pharmacokinetics/pharmacodynamics

6.3.1 Pharmacokinetics

Analyses will be performed on the Pharmacokinetic analysis set. A pooled treatment group (all 800mg BID patients, regardless of study part or tumor type) will be included for PK analyses.

The concentration-times courses of all analytes will be tabulated for each cohort by treatment group. The following statistics will be calculated for each of the sampling points: arithmetic mean, standard deviation, and coefficient of variation (CV), geometric mean, geometric standard deviation (re-transformed standard deviation of the logarithms), minimum, median, maximum value, and the number of measurements. Means at any time will only be calculated if at least 2/3 of the individual data were measured and were above the lower limit of quantification (LLOQ). For the calculation of the mean value, a data point below LLOQ will be substituted by one half of this limit. In tables showing mean values, where values below LLOQ are included in the calculation of mean values, these means will be marked.

Individual and geometric mean concentration vs. time curves of all analytes (using the actual sampling times for individual plots and the planned sampling times for mean plots) will be plotted by cohort using both linear and semilogarithmic scale.

The amount and percent of drug excreted into urine will be graphically illustrated for the sampling interval as well as for the whole sampling period (bar-charts for the individual data and the arithmetic mean including standard deviation).

Pharmacokinetic characteristics (t_{max} , t_{last} , and $\%AUC(t_{last} - \infty)$ excluded) will be summarized by the statistics mentioned above. t_{max} and t_{last} will be described utilizing minimum, maximum, and median as well as frequency counts.

PK Dose proportionality

To investigate dose proportionality, an explorative ANOVA, including the factor cohort, will be performed on the log-transformed values of C_{max}/D , $AUC(0-t_{last})/D$, and AUC/D calculated from single (where applicable) and multiple dose PK profiles.

Bridging: tablet vs solution relative bioavailability

PK parameters of different dose levels will be analyzed together for the assessment of relative bioavailability.

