In order to evaluate the relative bioavailability of the tablet formulation, tablet C_{max}/D , $AUC(0-t_{last})/D$, and AUC/D on Cycle 1, Day -3 will be compared to solution C_{max}/D , $AUC(0-t_{last})/D$, AUC/D on Cycle 1, Day 1 for all analytes. If needed, additional PK parameters may be used for relative bioavailability assessment. The logarithms of these PK parameters will be analyzed using analysis of variance (ANOVA) including subject and formulation effects.

Based on these analyses, point estimates (LS-means) and exploratory 90% confidence intervals for the ratios (tablet/solution) of C_{max}/D , $AUC(0-t_{last})/D$, and AUC/D will be calculated by re-transformation of the logarithmic data using the intra-individual standard deviation of the ANOVA.

Subjects to be included in the relative bioavailability evaluation ("tablet bridging cohort") should have evaluable pharmacokinetic data on both Cycle 1, Day -3 and Cycle 1, Day 1.

Food effect

Statistical Analysis Plan

Protocol No.: **BAY 1163877/16443**

Page: 16 of 20:

In order to evaluate the effect of food on BAY 1163877, C_{max} and $AUC(0-t_{last})$ on Cycle 1, Day -3 and C_{max} and $AUC(0-t_{last})$ on Cycle 1, Day 1 will be compared. The logarithms of C_{max} and $AUC(0-t_{last})$ will be analyzed using ANOVA including subject and food effect.

Based on these analyses, point estimates (LS-means) and exploratory 90% confidence intervals for the ratios (high-fat, high-calorie meal / fasting) of C_{max} and $AUC(0-t_{last})$ will be calculated by re-transformation of the logarithmic data using the intra-individual standard deviation of the ANOVA.

The PK parameters C_{max}/D , $AUC(0-t_{last})/D$, AUC/D , C_{max} and $AUC(0-t_{last})$ will be graphically illustrated using stickplots. Scatterplots of the PK parameters C_{max}/D , $AUC(0-t_{last})/D$, AUC/D will be created.

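### The exploratory dose-proportionality ANOVA has cohort as its only named factor while formulation changes between the 200 and 400 mg/day groups, so part of its result cannot tell dose from formulation (low severity)

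*SAP*

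**What the plan says.** References are to the current SAP (the supplement approved 11 Dec 2019).

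- **Dose proportionality, section 6.3.1.** "To investigate dose proportionality, an explorative ANOVA, including the factor cohort, will be performed on the log-transformed values of" Cmax/D, AUC(0-tlast)/D and AUC/D, from single-dose (where applicable) and multiple-dose profiles. No other factor is named, and the analysis is not limited to one formulation.
- **Groups, section 4.1.** The formulation changes between the second and third escalation groups, from "200 mg BAY 1163877 (100 mg solution BID") to "400 mg BAY 1163877 (200 mg tablet BID"). The 100 mg/day group is also solution; the 800, 1200 and 1600 mg/day groups are also tablet.
- **Pooling, section 6.3.1.** "A pooled treatment group (all 800mg BID patients, regardless of study part or tumor type) will be included for PK analyses". This enlarges one tablet dose level only.
- **Bridging, section 6.3.1.** Tablet on Day -3 and solution on Day 1 are compared within subject on the same three parameters, "analyzed using analysis of variance (ANOVA) including subject and formulation effects", with exploratory 90% CIs for the ratio. Section 3 sets the minimum: "pharmacokinetic data are needed in a minimum of 3 subjects for relative bioavailability assessment".
- **Switching, section 3.** Depending on the bridging result, "subjects who initially start with solution formulation may be switched to tablet formulation in later cycles".
- **Objective, section 2.** One primary objective is "To characterize the pharmacokinetics (PK) of BAY 1163877".

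**The concern.** If the tablet delivers a different fraction of the dose than the solution, exactly proportional PK still shows a step in Cmax/D and AUC/D between 200 and 400 mg/day. A cohort-only ANOVA counts that step as a cohort difference, and the natural reading of a cohort difference in this analysis is non-proportionality. The error can also run the other way: a tablet with higher bioavailability can mask a real fall in dose-normalised exposure.

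This is the SAP's only dose-proportionality analysis, and PK characterisation is a primary objective. The plan itself treats the tablet/solution ratio as unknown, since it sets up a bridging comparison to estimate it, but section 6.3.1 does not say that the two results are to be read together. At stake is one exploratory PK statement. Dose selection rests on the DLT model in section 6.5, and the bioavailability estimate is made within subject; neither is touched.

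**Working it through.** The SAP gives no sample size, test level or expected ratio for this analysis, so there is no planned figure to reproduce.

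**Step 1: can the two effects be separated?** Six cohort indicators give a design of rank 6. Adding a tablet indicator gives seven columns, still of rank 6, because the tablet column is the sum of the four tablet-cohort columns. With the section 4.1 groups, formulation is aliased with cohort, so a formulation term beside cohort would not help.

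**Step 2: how often would a formulation difference alone make the cohort test significant?** From the SAP: six groups (two solution, four tablet) and 3, optionally 4, subjects per dose level. Assumed: tablet/solution ratio R from 0.70 to 1.40, between-subject CV 30-50%, 5% level, exactly proportional PK.

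Log-scale variance is s² = ln(1+CV²): 0.0862 at CV 30%, 0.2231 at CV 50%. Group means are 0 (solution) and ln R (tablet). With n per cohort the noncentrality is

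λ = n[2(2/3)² + 4(1/3)²](ln R)²/s² = (4/3)·n·(ln R)²/s²,

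with 5 and 6(n-1) degrees of freedom.

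- R = 0.80, n = 4, CV 30%: (ln 0.80)² = 0.0498, λ = (4/3)·4·0.0498/0.0862 = 3.08, critical F(5,18) = 2.77, rejection rate 0.178.
- R = 0.80, n = 3, CV 50%: λ = (4/3)·3·0.0498/0.2231 = 0.89, critical F(5,12) = 3.11, rejection rate 0.078.

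Rejection rates of the overall cohort test over CV 30-50% and n = 3-4:

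| Ratio | Six cohorts of 3-4 | Top cohort of 20, others 3-4 |
|---|---|---|
| 1.00 | 5% | 5% |
| 0.90 or 1.10 | 6-7% | not computed |
| 0.80 or 1.25 | 8-18% | 10-23% |
| 0.70 or 1.40 | 12-43% | 16-57% |

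The last column illustrates the pooled 800 mg BID group entering as the top cohort; 20 is an assumed size. A direct solution-versus-tablet contrast, which the SAP does not plan, would reject more often: 14-38% at ratio 0.80 with cohorts of 3-4.

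Within the tablet cohorts, or within the solution cohorts, ln R cancels, λ = 0, and the rate stays at 5% for every ratio.

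**Step 3: masking.** Suppose dose-normalised exposure truly falls by a factor 2^-0.25 = 0.84 (16%) per doubling of dose. The six-group test is significant in 24-79% at ratio 1.00 and in 12-39% at ratio 1.25 (cohorts of 3-4, CV 30-50%).

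**Step 4: what the bridging ratio can settle.** The 90% CI around a ratio of 1 is exp(±t(0.95, n-1)·s·√(2/n)). At an assumed intra-subject CV of 25%, s = √ln(1.0625) = 0.246. With 3 subjects: 2.920·0.246·√(2/3) = 0.587, giving 0.56-1.80. With 6 subjects it is 0.75-1.33; with 8, 0.79-1.26.

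**Step 5: what a tablet-only test would lose.** For the same 16% fall per doubling and ratio 1, the four tablet cohorts (400-1600 mg/day, 4-fold) are significant in 9-22%, against 24-79% for all six (100-1600 mg/day, 16-fold). With 20 in the top cohort it is 14-40% against 50-98%.

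**Step 6: width of within-formulation ratios.** For two tablet cohorts, with s pooled over four cohorts, the 90% CI around 1 is exp(±t(0.95, 4(n-1))·s·√(2/n)). For n = 3 (t = 1.860) it is 0.64-1.56 at CV 30% and 0.49-2.05 at CV 50%. For n = 4 (t = 1.782) it is 0.69-1.45 and 0.55-1.81.

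**The case against.** The strongest reply is that nothing depends on this analysis. It is labelled exploratory, with no test level, hypothesis or decision rule, so the 5% used above is the reviewer's. The ratio is unknown, and close to 1 the distortion disappears. Section 4.1 puts the formulation in every escalation group label, and section 6.3.1 already provides a within-subject tablet/solution ratio with a 90% CI for the same parameters. A careful reader of the report could recognise a step between 200 and 400 mg/day. All of this stands, and it is why the point is minor.

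The bridging data may also be richer than the minimum of 3 subjects. Section 6.3.1 speaks of analysing different dose levels together for relative bioavailability, although section 3 places bridging in one escalation cohort, and the SAP does not say which. If several levels bridged, both formulations would exist at the same dose and the aliasing would be incomplete. That possibility is fair, but section 6.3.1 does not bring such data into the dose-proportionality model.

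Two further replies carry less or different weight. The wording does not strictly exclude other factors, but none is named, and formulation beside cohort could not be estimated from the listed groups. Classing each profile by the formulation taken that day is routine detail that may sit in the company guidelines the SAP cites; its absence is not an error.

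A reader might infer that the dose-proportionality assessment is invalid and should be replaced by a tablet-only test. The documents do not support that. Within-formulation contrasts are clean, and tablet-only as the main test would give up much of the sensitivity to real non-proportionality.

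**Conclusion.** The point holds at low severity. With cohort as the only named factor and the section 4.1 groups as listed, the overall test and any solution-versus-tablet contrast cannot separate dose from formulation. Under exact proportionality the overall test would be significant in 6-7% at ratios of 0.90 or 1.10 and in 8-18% at 0.80 or 1.25. These figures assume between-subject CV 30-50%, 3-4 subjects per cohort and a 5% level, none of which the SAP fixes for this analysis except the initial cohort size. Higher rates need a ratio further from 1 or a much larger top cohort.

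A reader might also infer that the plan will wrongly report non-proportional PK. That would require a tablet/solution ratio away from 1, and the document gives no estimate of it.

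**What to change.** In section 6.3.1:

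1. Keep the all-cohort ANOVA as planned.
2. Add a within-formulation analysis: tablet profiles at 400 to 1600 mg/day, and solution profiles at 100 versus 200 mg/day, reported as dose-normalised cohort ratios with 90% CIs. Assign each profile to the formulation actually taken.
3. State that a step between the solution and tablet groups will not be attributed to non-proportionality without reading it against the bridging tablet/solution ratio and its 90% CI.

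The cost is a few sentences and one more exploratory analysis, with no new data. The added intervals will be wide, and with 3 bridging subjects the comparison in item 3 may be inconclusive; the report should then say so. Tablet-only should not become the main test.

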6.3.2 Pharmacodynamic data

Cardiovascular parameters will be described by the following summary statistics: arithmetic mean, standard deviation, median, minimum and maximum. These summary statistics will be presented by cohort for the original data as well as for the difference to baseline (defined as the pre-dose assessment of the day being analyzed), if applicable.

Graphical displays of individual data as well as mean values with standard deviation may be included for absolute values as well as change from baseline.

6.4 Safety

The analyses will be performed on the safety analysis set and results will be displayed by region (Asia, ROW, and total), if reasonable.

6.4.1 Study drug exposure

Duration of treatment will be summarized using summary statistics. Actual dose, total amount of dose, and percent of planned dose during study period will be also summarized. Dose modification with reason will be summarized.

6.4.2 Maximum tolerated dose

Individual listings of DLTs with CTCAE v4.03 code and grade will be presented.

The incidence of subjects with DLTs during Cycle 1 will be summarized by treatment and, if possible, modeled as a function of BAY 1163877 dose using Bayesian logistic regression. The moderately-informative independent priors used during the interim dose response analysis (see Section 6.5 for details) as well as non-informative priors will be used for this analysis to assess sensitivity of the estimates. Parameter estimates and model predictions will be reported with 90% credibility sets. The MTD will be computed as a derived function of model parameters as:

$$MTD = (\log(0.2/0.8) - \text{intercept})/\text{slope}.$$

The posterior distribution of the MTD will be summarized in tabular and graphical formats.

6.4.3 Adverse Events

Adverse events will be analyzed using the National Cancer Institute (NCI) Common Terminology Criteria for Adverse Event (CTCAE) version 4.03. In addition a separate set of AE tables will be generated using MedDRA terms.

Statistical Analysis Plan

Protocol No.: **BAY 1163877/16443**

Page: 17 of 20:

The incidence of treatment-emergent adverse events (TEAEs), drug-related adverse events (TEADRs), treatment-emergent and drug-related serious adverse events (SAEs), respectively, will be summarized by treatment group CTCAE body system code and worst NCI-CTCAE grade. TEAEs, SAEs, drug-related TEAEs, and drug-related SAEs for events of Grade 3/4/5 will be summarized similarly.

AEs are considered treatment emergent if they have started or worsened after the first study drug administration up to 30 days after the end of treatment with study drug.

Frequency tables will also be provided for the changes of CTCAE grade from pre-treatment and changes of worst CTCAE grade under treatment.

In addition, TEAEs, SAEs, drug-related TEAEs, and drug-related SAEs will be summarized by MedDRA (Version 20.1 or later) system organ class, preferred term and worst NCI-CTCAE grade. The same will be also summarized similarly for events of Grade 3/4/5.

Patient listings of all AEs, SAEs, AEs leading to dose reduction, AEs leading to dose interruption, AEs leading to discontinuation, dose limiting toxicity AEs, and deaths will be presented.

